13.0 BLINDED INTERIM ANALYSIS

A blinded interim analysis will be conducted when approximately 75% of randomized subjects have either completed the study or discontinued from the study. The blinded interim analysis is to obtain an estimate of the pooled standard deviation of the change from baseline in the PARS score to Week 8 of the double-blind acute treatment period. The sample size will be re-estimated using simulation in the same manner as the original sample size as described in Section 14 using the estimated pooled standard deviation and dropout rate from the blinded interim analysis. If the estimated pooled standard deviation is larger than the assumed pooled standard deviation due to assumption deviation as well as COVID-19 remote visits or dropout rate is increased, the sample size in placebo and escitalopram treatment groups may be increased to ensure an adequate power. However, due to the difficulties in recruiting pediatric subjects with GAD, the number of subjects in each treatment arm will be capped at 160.

As the sample size re-estimation requires only the pooled standard deviation and dropout rate to be updated, all data and personnel will remain blinded for the interim analysis. Randomization code will not be released for the sample size re-estimation. There are no potential unblinding issues in the sample size re-estimation. As this is a blinded re-estimation, there is no impact on the overall Type I error rate of the study.

SAP SCT-MD-60 Allergan

Page 40 of 53

14.0 DETERMINATION OF SAMPLE SIZE

The sample size estimate was constructed using a simulation approach as described in Lu K. (2012).

The primary efficacy parameter is the change from baseline to Week 8 of the double-blind acute treatment period in PARS total score. To detect an effect size (treatment group difference of 2.30 units relative to pooled standard deviation of 5.79) of 0.39, a sample size of 128 subjects in the escitalopram treatment group and 128 subjects in the placebo group will provide 85% power based on an MMRM model using simulation method. The simulation assumed a correlation of 0.7 between the repeated measures, and a common dropout rate of 14%, based on historical data of escitalopram in pediatric subjects.

SAP SCT-MD-60 Allergan

Page 41 of 53

15.0 STATISTICAL SOFTWARE

Statistical analyses will be performed using version 9.4 (or newer) of SAS.

Page 42 of 53

16.0 DATA HANDLING CONVENTIONS

16.1 VISIT TIME WINDOWS

Table 16.1–1 and Table 16.1–2 present the visits assigned for efficacy and safety analyses and the corresponding ranges of treatment days (window) during which an actual visit may occur.

Table 16.1–1. Visit Time Windows

Derived Visit	Scheduled Visit (Day) ^a	Window
Baseline ^b	Week 0 (Day 1)	Days ≤ 1
Week 1	Week 1 (Day 8)	Days [2, 11]
Week 2	Week 2 (Day 15)	Days [12, 21]
Week 4	Week 4 (Day 29)	Days [22, 35]
Week 6	Week 6 (Day 43)	Days [36, 49]
Week 8	Week 8 (Day 57)	$Days \geq 50 \ days \ and \ within \ double-blind \ acute \\ treatment \ period$
End of double-blind acute treatment period ^c	Final or termination visit du	ring the double-blind acute treatment period

a Relative to the date of the first dose of double-blind investigational product. Day 1 = the date of the first dose of double-blind investigational product.

Table 16.1–2. Visit Time Windows for the Double-Blind Down-Taper Period

Derived Visit	Scheduled Visit	Window
Week 9/Down-Taper Period	Week 9	Within the double-blind down-taper period (from 1 day after the end of double-blind acute treatment period to the end of the double-blind down-taper period)
End of double-blind down-taper period ^a	Final or termination vi	sit during the double-blind down-taper period

a Presented in analysis tables for safety parameters collected during the double-blind down-taper period. If any assessments are repeated at the end-of-double-blind-down-taper-period visit or during any visit window, the algorithm in Section 16.3 will be used to determine which values are used in the analysis.

b The window for selecting baseline values is from 30 days before the first dose of double-blind investigational product to Day 1.

c Presented in analysis tables for safety parameters, including but not limited to electrocardiograms, clinical laboratory values, vital signs, and C-SSRS. If repeated assessments occur at the end of double-blind acute treatment period visit or during any visit window, the algorithm in Section 16.3 will be used to determine which values are used in the analysis.

Page 43 of 53

If the visit date is on or after the date of the first dose of double-blind investigational product, the study day is calculated by visit date – date of the first dose of double-blind investigational product + 1. If the visit date is before the date of the first dose of double-blind investigational product, the study day is calculated by visit date – date of the first dose of double-blind investigational product. Therefore, a negative day indicates a day before the start of the double-blind investigational product.

If a subject has 2 or more visits within the same window, the last visit with a nonmissing value will be used for analysis.

16.2 AGE-AND-GENDER-CORRELATED VALUES FOR WEIGHT AND HEIGHT

To adjust weight (kg) and height (cm) for sex and age, one needs to compare them to standard reference values for the same sex and age group, which are available in the United States Growth Charts and can be downloaded from: http://www.cdc.gov/growthcharts/percentile_data_files.htm

The z-score is calculated as below

$$z = \frac{(X/M)^L - 1}{SL}$$
, if L \neq 0 and

$$z = \frac{\ln(X/M)}{S}$$
, if $L = 0$,

where X is the physical measurement (e.g. weight and height) and L, M and S are the values from the appropriate table corresponding to the age in months (or length/stature) and sex (1 = male; 2 = female). X must be in metric measurements (kilograms or meters). This is called LMS method (Cole TJ, 1990), and parameters L, M, and S are the Box-Cox transformation power, median, and standard deviation, respectively, in the reference data, which again are provided in the reference data tables.

SAP SCT-MD-60 Allergan

Page 44 of 53

16.3 REPEATED OR UNSCHEDULED ASSESSMENTS OF SAFETY PARAMETERS

If a subject has repeated assessments before the date of first dose of double-blind investigational product, the results from the final nonmissing assessment made before the date of the first dose of double-blind investigational product will be used as baseline. If end-of-double-blind-treatment period assessments are repeated or if unscheduled visits occur, the last nonmissing post-baseline assessment during the double-blind acute treatment period will be used as the end-of-double-blind-acute-treatment-period assessment for generating summary statistics. Likewise, if end of double-blind down-taper period assessment during the double-blind down-taper period will be used as the end-of-double-blind-down-taper-period assessment for generating summary statistics.

Similarly, if a subject has repeated assessments within a given visit window, the last non-missing post-baseline assessment during the window will be used as the assessment for that visit window when generating summary statistics.

However, all post-baseline assessments will be used to determine PCS values for laboratory parameters, vital signs and ECG parameters, and to determine most severe suicidal ideation and most severe suicidal behavior from C-SSRS. All assessments will be presented in the data listings.

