9.1.2 Baseline Visit (Visit 2)

The following procedures will be performed at the Baseline Visit:

- Reassess for eligibility against the inclusion and exclusion criteria.
- Randomization will take place for eligible subjects and each will receive a randomization number.
- Record any AEs that have occurred since the previous visit and any changes in concomitant medications.
- Complete CGAS, PARS, and CGI-S.
- Complete C-SSRS.
- Complete global COVID-19 impact assessment.
- Record vital signs (blood pressure, pulse rate, temperature, and respiration rate).
- Perform a urine pregnancy test, if applicable.

When all the baseline procedures have been performed and the investigator has confirmed the subject's eligibility for the study, the study drug will be dispensed to the subject. Subjects should take their first dose of study drug in clinic on Day 1.

Refer to [Section 8.1.3](#) for procedures and assessments if Visit 2 is done remotely. For remote visits, subjects will receive and take their first dose of study drug via curbside (preferred) or they will receive it by courier and take it at home.

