11.6 Safety Analysis

The safety analysis will be performed for the double-blind treatment period and double-blind down taper period separately using the Safety Population. The safety parameters will include AEs, clinical laboratory parameters, vital sign measurements, and ECG parameters. For each safety parameter, the last assessment made before the first dose of double-blind investigational product will be used as the baseline for all analyses of that safety parameter.

Safety data collected outside of planned visit windows but within allowance limits (up to 1 week late for Visits 7 and 8) will be included in the summary tables. Safety data collected outside of planned visit windows and outside of the allowance limits (>1 week to 6 weeks late for Visits 7 and 8) will be listed, but will not be included in the summary tables. Subgroup analyses may be performed to assess the impact of COVID-19 on the safety analyses.

The safety endpoints during the double-blind treatment period are as follows:

- Incidence of treatment-emergent adverse events (TEAEs).
- Observed values and change from baseline in vital signs (blood pressure, pulse rate, temperature, respiration rate, height, weight, BMI, height percentile, weight percentile, and BMI percentile); incidence of vital sign potentially clinically significant (PCS) values.
- Observed values and changes from baseline in ECG intervals and interpretation; incidence of ECG PCS values.
- Observed values and changes from baseline in clinical laboratory assessments (hematology, chemistry, and urinalysis); incidence of clinical laboratory PCS values.
- Incidence of suicidal ideation and/or suicidal behavior as determined by the C-SSRS.

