9.2.8 Analysis of COVID-19 impact assessment score

The global COVID-19 impact assessment will be used to evaluate the impact of the coronavirus disease pandemic on the severity of the subject's GAD during the last 1 week. The rating will include scores from 0 (not applicable, subject not enrolled in the trial during the pandemic) to 7 (extreme impact). Raters will also evaluate whether the impact was an improvement or worsening of the subject's GAD.

Subjects with scores from 4 (moderate impact) to 7 (extreme impact) at any visit other than the Screening Visit will be considered to have been significantly impacted, regardless of the direction of impact.

Number and percentage of subjects with each score on the global COVID-19 impact assessment will be summarized descriptively at each visit by treatment group for the mITT population, including subjects that were significantly impacted. For each score from 2 to 7, the number and percentage of subjects who improved or worsened will also be summarized.

Page 29 of 53

Page 30 of 53

10.0 SAFETY ANALYSES

The safety analysis will be performed for the double-blind acute treatment period and the double-blind down-taper period separately, using the Safety Population unless stated otherwise.

The safety parameters include adverse events (AEs), clinical laboratory parameters, vital signs, electrocardiographic (ECG) parameters, and suicide risk assessment using the Columbia-Suicide Severity Rating Scale (C-SSRS). For each safety parameter, the last non-missing safety assessment before the first dose of double-blind investigational product will be used as baseline. Continuous variables will be summarized by number of subjects and mean, SD, median, minimum, and maximum values. Categorical variables will be summarized by number and percentage of subjects.

Safety data collected outside of planned visit windows but within allowance limits (up to 1 week late for Visits 7 and 8) will be included in the summary tables. Safety data collected outside of planned visit windows and outside of the allowance limits (>1 week to 6 weeks late for Visits 7 and 8) will be listed, but will not be included in the summary tables. Subgroup analyses may be performed to assess the impact of COVID-19 on the safety analyses; details are listed in each safety section.

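### For subjects with repeat vital signs before Day 1, SAP 16.3 passes over the Day 1 pre-dose values that SAP 10.0 and protocol 11.6 take as baseline

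*SAP*

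**What the plan says.** SAP 16.3 deals with repeated and unscheduled safety assessments. Its first sentence opens with a condition, "If a subject has repeated assessments before the date of first dose of double-blind investigational product", and then states that "the final nonmissing assessment made before the date of the first dose of double-blind investigational product will be used as baseline".

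The general safety baseline is set elsewhere and is tied to the dose, not to its date. SAP 10.0 says that "the last non-missing safety assessment before the first dose of double-blind investigational product will be used as baseline". Protocol 11.6 says that "the last assessment made before the first dose of double-blind investigational product will be used as the baseline for all analyses of that safety parameter".

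SAP Table 16.1-1 gives the baseline window as Days ≤ 1, with the footnotes "Day 1 = the date of the first dose of double-blind investigational product" and "The window for selecting baseline values is from 30 days before the first dose of double-blind investigational product to Day 1". The text after the tables adds that, of two or more visits in one window, the last with a nonmissing value is analysed.

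On conduct, protocol 9.1.2 puts vital signs and the C-SSRS at the Baseline Visit, has study drug dispensed once the baseline procedures are done, and adds: "Subjects should take their first dose of study drug in clinic on Day 1". SAP 17.0 lists one departure from the protocol's analyses, which concerns weight and height z-scores, and declares no other.

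**The concern.** An in-clinic Baseline Visit falls on the calendar date of the first dose. A rule requiring an assessment before that date cannot select a value from that visit, although the value was obtained before any drug was taken. When the condition in SAP 16.3 is met, its baseline is an older value, and the result differs from the one given by SAP 10.0 for the same subject.

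Two things are at stake for those subjects. The first is change from baseline in vital signs, together with the potentially clinically significant (PCS) flags, which need a change criterion as well as an observed-value criterion. The second is the status of the Day 1 value itself. If baseline is an earlier visit, the Day 1 pre-dose reading comes after baseline but before drug. It sits in no post-baseline window, since Week 1 starts on Day 2, yet SAP 16.3 uses all post-baseline assessments to find PCS values. A programmer could count it as an on-treatment finding.

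**Working it through.** The plan gives no figure to reproduce; this is a comparison of rules.

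**Step 1: put the rules on the study-day scale.** SAP 16.1 computes the study day as visit date − first-dose date + 1 on or after the first dose, and without the + 1 before it. The first-dose date is therefore Day 1, the day before is Day −1, and there is no Day 0. An assessment before the *date* of first dose has study day ≤ −1. One before the *dose* may be on Day 1.

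| Source | Safety baseline | Can a Day 1 pre-dose value be chosen? |
|---|---|---|
| Protocol 11.6 | Last before the first dose | Yes |
| SAP 10.0 | Last nonmissing before the first dose | Yes |
| SAP Table 16.1-1 | Days ≤ 1 | Yes |
| SAP 16.1, several visits in a window | Last nonmissing in the window | Yes |
| SAP 16.3, if repeats exist before the first-dose date | Final nonmissing on study day ≤ −1 | No |

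**Step 2: apply them to two kinds of in-clinic subject.**

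- *One Screening value and one Day 1 pre-dose value.* Only one assessment lies before the first-dose date, so there is no repeat before that date. The condition in 16.3 is not met, and SAP 10.0 gives Day 1.
- *Screening, a repeat or unscheduled assessment before Day 1, and a Day 1 pre-dose value.* Two assessments lie before the first-dose date, so the condition is met. SAP 16.3 gives the later of those two; the other four rules give Day 1.

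Screening runs from Day −21 to Day −1, and Day −k is k calendar days before Day 1. The baseline chosen by 16.3 is therefore between 1 and 21 days older than the Day 1 value.

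**Step 3: which parameters can differ.** By the schedule in SAP 3.2, the vital signs measured at both Screening and Baseline are blood pressure, pulse, temperature and respiration. ECG, chemistry, hematology, urinalysis, height, weight and BMI have no scheduled Day 1 value. The C-SSRS is measured on Day 1, but SAP 10.5 summarises it by period (lifetime, acute treatment, down-taper), not as change from baseline. A remote Baseline Visit includes no vital signs (SAP 3.3), so it yields no Day 1 value to lose.

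**Step 4: how a flag can switch.** Under SAP Table 10.3-1, a high systolic flag at ages 12–17 needs a value ≥ 140 mm Hg and a rise ≥ 20. For a post-baseline reading of exactly 140, the rise criterion is met only if baseline ≤ 140 − 20 = 120. At ages 7–11 the corresponding cut is 125 − 20 = 105. If the earlier value and the Day 1 value lie on opposite sides of that cut, the two rules disagree on the flag, in either direction. The same applies to diastolic pressure and pulse with their change criterion of 15. Temperature and respiration have no PCS criterion in that table, so only their change-from-baseline summaries are affected.

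**The case against.** The strongest reply is that 16.3 is only a tie-break for repeats, and that the intended baseline is plain from four other provisions. If its wording is read loosely, so that an assessment before the date of dosing means any pre-dose assessment, Screening and Day 1 are themselves the repeats and the final one is Day 1. If it is read strictly, the usual subject never triggers it. On either consistent reading the usual subject has a Day 1 baseline. That stands. It does not remove the conflict for a subject with a repeat before Day 1, for whom the strict wording selects an older visit.

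A reader might infer more: that every in-clinic subject loses the Day 1 value, because vital signs are always measured at both Screening and Baseline, and because a footnote to Table 16.1-1 begins "If repeated assessments occur at the end of double-blind acute treatment period visit or during any visit window, the algorithm in Section 16.3". The documents do not support this. The inference counts Day 1 as before the first-dose date in order to meet the condition, then denies it in order to exclude the value. The footnote belongs to the end-of-treatment row, and the by-window rule in 16.3 concerns post-baseline assessments, so it cannot define a baseline.

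It is also fair to say that the safety analyses are descriptive and that the rule applies alike to both arms. The documents give no basis for putting a size on added noise or regression to the mean. Finally, Days ≤ 1 in Table 16.1-1 does not by itself require a pre-dose value, so the table alone is not a sufficient model for the correction.

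**Conclusion.** The inconsistency is real but minor. As written, SAP 16.3 gives a different safety baseline from SAP 10.0, protocol 11.6, Table 16.1-1 and the last-visit rule in SAP 16.1, and SAP 17.0 does not declare the difference. It reaches subjects with an in-clinic Baseline Visit and more than one vital-sign assessment before Day 1. Their number is not given in the documents and cannot be derived from them; the full randomized sample is not a defensible estimate.

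Within that subset the effect is on change from baseline in blood pressure, pulse, temperature and respiration, and on blood pressure and pulse PCS flags. Efficacy analyses are unaffected, since SAP 9.0 defines their baseline separately. The conclusion assumes that the condition in 16.3 is read as written and that Baseline Visit vital signs precede the first dose, as the order of procedures in protocol 9.1.2 implies.

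**What to change.** In the first sentence of SAP 16.3, replace both references to the date of first dose, in the condition and in the rule, with *before the first dose (including pre-dose assessments on Day 1)*. Screening and Day 1 then count as repeats, the final one is Day 1, and the sentence agrees with SAP 10.0 and protocol 11.6. It also follows that a Day 1 pre-dose value is the baseline and is not counted as post-baseline. It would help to add that in-clinic Baseline Visit assessments are taken as pre-dose by the order of procedures in protocol 9.1.2.

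The cost is a wording change in one SAP sentence. No data collection, visit or site procedure changes.

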16.4 MISSING DATE OF THE LAST DOSE OF INVESTIGATIONAL PRODUCT

When the date of the last dose of investigational product in the study taken during the double-blind acute treatment period is missing for a subject in the Safety Population, all efforts should be made to obtain the date from the Investigator. If it is still missing after all efforts, then the last available dosing record date will be used as the last dose date.

16.5 MISSING SEVERITY ASSESSMENT FOR ADVERSE EVENTS

If severity is missing for an AE that started before the date of the first dose of double-blind investigational product, an intensity of mild will be assigned. If severity is missing for an AE that started on or after the date of the first dose of double-blind investigational product, an intensity of severe will be assigned. The imputed values for severity assessment will be used for the incidence summary. The number of imputed severity value will be presented in the footnote of the incidence summary. The imputed values will be shown as missing in the data listings.

Page 45 of 53

16.6 MISSING CAUSAL RELATIONSHIP TO INVESTIGATIONAL PRODUCT FOR ADVERSE EVENTS

If the causal relationship to the investigational product is missing for an AE that started on or after the date of the first dose of double-blind investigational product, a causality of Likely/Certain will be assigned. The imputed values for causal relationship to double-blind treatment will be used for the incidence summary. The number of imputed severity value will be presented in the footnote of the incidence summary. The imputed values will be shown as missing in the data listings.

16.7 MISSING DATE INFORMATION FOR ADVERSE EVENTS

The following imputation rules only apply to cases in which the start date for AEs is incomplete (i.e., partly missing).

Missing month and day

- If the year of the incomplete start date is the same as the year of the first dose of double-blind investigational product, the month and day of the first dose of double-blind investigational product will be assigned to the missing fields
- If the year of the incomplete start date is before the year of the first dose of double-blind investigational product, *December 31* will be assigned to the missing fields
- If the year of the incomplete start date is after the year of the first dose of double-blind investigational product, *January 1* will be assigned to the missing fields

Missing month only

• If only the month is missing, the day will be treated as missing and both the month and the day will be replaced according to the above procedure

Missing day only

- If the month and year of the incomplete start date are the same as the month and year of the first dose of double-blind investigational product, the day of the first dose of double-blind investigational product will be assigned to the missing day
- If either the year of the incomplete start date is before the year of the date of the first dose of double-blind investigational product or if both years are the same but the month of the incomplete start date is before the month of the date of the first dose of double-blind investigational product, the last day of the month will be assigned to the missing day

Page 46 of 53

• If either the year of the incomplete start date is after the year of the date of the first dose of double-blind investigational product or if both years are the same but the month of the incomplete start date is after the month of the date of the first dose of double-blind investigational product, the first day of the month will be assigned to the missing day

If the stop date is complete and the imputed start date as above is after the stop date, the start date will be imputed by the stop date.

If the start date is completely missing and the stop date is complete, the following algorithm will be used to impute the start date:

- If the stop date is after the date of the first dose of double-blind investigational product, the date of the first dose of double-blind investigational product will be assigned to the missing start date
- If the stop date is before the date of the first dose of double-blind investigational product, the stop date will be assigned to the missing start date

